### 3.3. Dose Rationale

Two doses of RVT-101 will be evaluated in the proposed Phase 2 clinical study: 35 mg and 70 mg. The 35 mg dose of RVT-101 has been evaluated in multiple clinical studies in healthy volunteers and Alzheimer's disease patients. This dose has been safe and well-tolerated in all clinical studies to date.

The rationale for evaluating a 70 mg dose of RVT-101 is based on its modest antagonist activity against the 5-HT2a receptor which has been estimated to be 1/40th as potent as its primary activity against the 5-HT6 receptor. The 5-HT2a receptor has been implicated in the pathophysiology underlying visual hallucinations in Lewy body diseases, with preservation of 5-HT2 receptors in the temporal cortex differentiating hallucinating and non-hallucinating DLB cases ([Cheng et al., 1991](#)). Given that RVT-101 has a lower affinity for the 5-HT2a receptor than the 5-HT6 receptor, it is reasonable to evaluate higher doses in a population that could benefit from 5-HT2a receptor antagonism. In addition, it is possible that greater benefit from the effect on the 5-HT6 receptor could also be observed since the efficacy of doses higher than 35 mg has not been previously assessed.

RVT-101 has been administered in 18 completed Phase 1 studies. In these studies, a total of 398 subjects received RVT-101, with a further 64 subjects receiving either placebo alone or another treatment. Single doses up to 175 mg have been administered to healthy adult subjects. Multiple doses up to 70 mg daily for 10 days in healthy elderly subjects (ages 60 to 77) and up to 50 mg daily for 13 days in younger subjects (ages 22 to 45) have been administered. Approximately 213 subjects received doses greater than 35 mg as single or repeat doses. Four Phase 2 studies in mild to moderate Alzheimer's disease have been completed. These include 3 monotherapy studies (Studies AZ3100603, AZ3106242, and AZ3110865) and 1 adjunctive therapy study in subjects on background donepezil (Study AZ3110866). In addition, one Phase 3 study has been completed; a double-blind, placebo controlled study in subjects with mild or moderate Alzheimer's disease (RVT-101-3001). A 12-month open-label extension study to RVT-101-3001 is ongoing (RVT-101-3002).

In completed Phase 2 clinical studies to investigate the efficacy and safety of RVT-101 as monotherapy in subjects with mild to moderate Alzheimer's disease, 591 subjects have received RVT-101. In the completed Phase 2b and Phase 3 clinical studies to investigate the efficacy and safety of RVT-101 as adjunctive therapy to stable donepezil therapy in subjects with mild to moderate Alzheimer's disease, 1113 subjects received RVT-101.

The data from completed studies suggest that the compound is well tolerated and there were no safety issues or trends identified that would preclude further studies with RVT-101.

The Phase 1 study (RVT-101-1001) investigated the PK and safety of RVT-101 in healthy elderly subjects at doses of 35 mg and 70 mg once daily for 7 days (Part 1) and the food effect on 35 mg (Part 2). Data from Part 1 in subjects receiving the 70 mg dose show that this dose was well-tolerated; there were no Grade 2-4 AEs, SAEs, or withdrawals due to AEs. One minor (Grade 1) adverse event was reported (dry mouth) which was considered related to study drug by the investigator and which resolved without any interruption of treatment. There were no clinically significant changes in vital signs, laboratory values, or ECGs. This supports the use of 70 mg in the current study in subjects with DLB.

#### 4. OBJECTIVES AND ENDPOINTS

Objective	Endpoint
Primary Efficacy	

 
To assess the effects of RVT-101 versus placebo on motor function as measured by the Unified Parkinson's Disease Rating Scale – Part III (UPDRS-III) after 24 weeks of treatment
 
	Change from baseline in the UPDRS-III total score at Week 24
Secondary Efficacy	

 
To assess the effects of RVT-101 versus placebo on cognition as measured by the ADAS-Cog 11 after 24 weeks of treatment
 
	Change from Baseline on ADAS-Cog 11 at Week 24

 
To assess the effects of RVT-101 versus placebo on global function as measured by the CIBIC+ after 24 weeks of treatment
 
	Total score of the CIBIC+ at Week 24
Tertiary Efficacy	

 
To assess the effects of RVT-101 versus placebo on activities of daily living as measured by the ADCS-ADL scale after 24 weeks of treatment
 
	Change from Baseline in the ADCS-ADL at Week 24

 
To assess the effects of RVT-101 versus placebo on the Basic and Instrumental subscores of the ADCS-ADL scale after 24 weeks of treatment.
 
	Change from Baseline in the Basic and Instrumental subscores of the ADCS-ADL at Week 24

 
To assess the effects of Intepirdine versus placebo on the Unified Parkinson's Disease Rating Scale – Part III, 5-item subscale (UPDRS-5) after 24 weeks of treatment
 
	Change from baseline in the UPDRS-5 total score at Week 24

 
To assess the effects of RVT-101 versus placebo on cognition as measured by the composite z-score of the 7-domains of the CDR computerized assessment system after 24 weeks of treatment (CDR System domains include Power of Attention, Continuity of Attention, Quality of Working Memory, Quality of Episodic Memory, Speed of Memory, Cognitive Reaction Time and Reaction Time Variability)
 
	Change from Baseline in the composite z-score combining the 7 domains of the CDR computerized assessment system at Week 24

 
To assess the effects of RVT-101 versus placebo on working memory as a measure of executive function as assessed by the COWAT after 24 weeks of treatment
 
	Change from Baseline in COWAT score at Week 24

 
To assess the effects of RVT-101 versus placebo on cognitive function as measured by a composite z-score combining the 7 domains for the CDR computerized assessment system and the COWAT after 24 weeks of treatment
 
	Change from Baseline in composite z-score combining the 7 CDR System domains plus the COWAT at Week 24

 
To assess the effects of RVT-101 versus placebo on hallucinations and delusions as measured by a 2-item subscore on the NPI which is the sum of the scores for the hallucinations and delusions domains (Parts A and B) after 24 weeks of treatment
 
	Change from Baseline in the sum of Parts A and B of the NPI at Week 24

 
To assess the effects of RVT-101 versus placebo on visual hallucinations as measured by the NEVHI after 24 weeks of treatment
 
	Change from Baseline on the total severity score and distress score of the NEVHI score at Week 24 for subjects with visual hallucinations

 
To assess the effects of RVT-101 versus placebo on fluctuations in cognition using the CAF after 24 weeks of treatment
 
	Change from Baseline in CAF severity score at Week 24 for subjects with cognitive fluctuations

 
To assess the effects of RVT-101 versus placebo on subject dependence using the DS after 24 weeks of treatment
 
	Change from Baseline on DS at Week 24
Safety	

 
To assess the safety and tolerability of RVT-101 after 24 weeks of treatment
 
	AEs, physical examinations, vital signs (including orthostatic changes in BP and HR), ECGs, routine clinical laboratory assessments, questionnaire for symptoms potentially associated with orthostasis, and C-SSRS.
Exploratory	

 
To assess the effects of RVT-101 versus placebo on quality of life as measured by the EQ-5D-5L after 24 weeks of treatment
 
	Change from Baseline on EQ-5D-5L at Week 24

 
To assess the effects of RVT-101 versus placebo on sleep-related behaviors as measured by the modified CSI
 
	Change from Baseline on CSI scores (Part I, Part II) at Week 24

 
To assess the effects of RVT-101 versus placebo on each domain of the CDR Computerized Assessment System after 24 weeks of treatment
 
	Change from Baseline on each domain of the CDR computerized assessment system at Week 24

 
To assess the effects of RVT-101 versus placebo on depression and anxiety as measured by a 2-item subscore on the NPI, which is the sum of the scores for the depression/dysphoria and anxiety domains (Parts D and E) after 24 weeks of treatment
 
	Change from Baseline in sum of Parts D and E of the NPI at Week 24

 
To estimate the pharmacokinetic (PK) parameters of RVT-101 and explore relationships to efficacy or safety endpoints, as appropriate
 
	Plasma concentrations and PK parameters ( $AUC_{TSS}$ , $C_{max-ss}$ and $C_{min-ss}$ ) for each subject

## **5. STUDY DESIGN**

### **5.1. Overall Design**

This is a multi-center, double-blind, randomized, placebo-controlled, parallel-group study in patients with probable DLB who are either not receiving therapy for DLB or are receiving a stable regimen of standard therapy for DLB. The efficacy and safety of RVT-101 at doses of 70 mg and 35 mg daily will be evaluated over a 24-week treatment period. All subjects who are on stable doses of other therapies to treat cognitive deficits and/or hallucinations associated with DLB will continue to remain on them for the duration of the study. Approximately 240 subjects will be randomized. The randomization ratio will be 1:1:1 (70 mg RVT-101: 35 mg RVT-101: placebo). The primary endpoint will be measured after 24 weeks of treatment. Study participation will last approximately 32 weeks: 0 to 4 weeks for Screening, a 2-week Single-Blind Run-In Period to evaluate baseline status, a 24-week randomized, double-blind, placebo-controlled Treatment Period and a 2-week Safety Follow-up Period for subjects who do not enter the extension study RVT-101-2002.

There will be weekly clinical assessments for the first two weeks of double-blind treatment, bi-weekly assessments thereafter until 12 weeks post-randomization and every six weeks thereafter. For certain visits (Visits 5, 7 and 9), subjects may have the option of whether to have assessments performed at the clinical study site or by a trained, visiting nurse in their own home.

[figure not shown]
An independent Safety Monitoring Committee (SMC) will review interim safety data accumulated after approximately 30 subjects have completed 4 weeks of double-blind treatment and throughout the study at points specified in the SMC Charter. The SMC will provide their recommendation regarding the acceptability of reducing the visit frequency by omitting certain visits (Visits 5, 7 and 9) for both newly enrolled subjects and subjects active in the study at the time of the recommendation. Study enrollment will not be stopped or slowed to wait for SMC's recommendation and will proceed as planned with all visits until the SMC recommendation is made. Site will be formally notified of the SMC's recommendation regarding whether or not Visits 5, 7 and 9 can be omitted.

After completion of Visit 12, the subject may be considered for enrollment in the extension study RVT-101-2002. If the subject does not enter the extension study, he/she will return for the Safety Follow-up Visit (Visit 13). Subjects who enter the extension study will not be required to complete Visit 13.

## 5.2. Study Schematic

The design of the study is illustrated in Figure 1.

**Figure 1 Study schematic**

Abbreviations: qd = daily; V = visit; WK = week

 Subjects will be given the option of whether to have assessments performed at the clinical study site or by a trained, visiting nurse in their own home. Also, if and when the DSMB approves a reduced visit frequency, Visits 5, 7 and 9 will be skipped.

 Safety Follow-up Visit (V13) is conducted only for subjects who do not enter the extension study.

## 6. SUBJECT POPULATION

### 6.1. Type and Number of Subjects

Approximately 240 subjects with probable DLB who are either not receiving therapy for DLB or who are taking a stable regimen of therapy(ies) for DLB will be enrolled.

In order to manage the total study enrollment, Axovant Sciences, may suspend screening and/or enrollment at any site or study-wide at any time.

With the exception of the determination required in inclusion criterion #1, all study assessments and determinations may be delegated by the investigator to a suitably qualified designee approved and documented for this study. Medical decisions must be made by a qualified physician. If the investigator is not a physician, he/she must delegate medical decisions to a qualified physician and consult a physician for medical issues related to eligibility.

### 6.2. Inclusion Criteria

Subjects eligible for enrollment in the study must meet all of the following criteria:

- 1) Male or female subject with a clinical diagnosis of DLB established for a minimum of 2 months prior to Visit 1 and who currently meet Consensus criteria (McKeith et al., 2005) for probable DLB as determined by the principal investigator by virtue of having dementia, defined as progressive cognitive decline of sufficient magnitude to interfere with normal social or occupational function, and either a) or b) below:
  - a) At least two of the following three Core features:
    - i) Fluctuating cognition with pronounced variations in attention and alertness,
    - ii) Recurrent visual hallucinations that are typically well-formed and detailed, or
    - iii) Spontaneous features of parkinsonism with a date of onset no greater than one year before the onset of the cognitive decline.
  - b) One of the Core features above and at least one of the following three Suggestive features:
    - i) REM sleep behavior disorder,
    - ii) Severe neuroleptic sensitivity, or
    - iii) Low dopamine transporter uptake in basal ganglia demonstrated by single photon emission computed tomography (SPECT) or positron emission tomography (PET) scan as determined by the investigator
- 2) Subject has an MMSE score of 14 to 26, inclusive, at Screening.

Note: Subject must also have an MMSE score of less than or equal to 26 at Visit 2 and an MMSE score of 14 to 26, inclusive, at the Baseline visit. Subjects not meeting these MMSE criteria at Visit 2 and the Baseline visit will be discontinued from the study.

In addition, the MMSE score at Baseline (Visit 3) must not have declined by 4 points or more from the Visit 2 MMSE score. For subjects with an MMSE score at Baseline (Visit 3) of 4 or more points lower than their Visit 2 MMSE score or an MMSE <14 at Visit 3, the Run-In period may be extended for 1 to 10 days. If, after the first extension to the Run-In Period, the subject still does not meet the MMSE stability criterion, the Run-In period may again be extended for an additional 1 to 10 days. No more than 2 extensions to the Run-In Period will be allowed. If this MMSE stability requirement is not met after 2 extensions of the Run-In Period, the subject will be discontinued from the study (see also [Section 8.1](#)).

- 3) If the subject is currently receiving any of the following medications, the treatment regimen has been stable (i.e., no changes in the type of drug, dose or frequency of dosing) for at least 30 days prior to the Screening Visit and there is no intent to change this treatment regimen for the duration of the study.
  - Acetylcholinesterase inhibitors (i.e., donepezil, galantamine, rivastigmine, tacrine)
  - Memantine
  - Axona® (caprylidene)
  - Antidepressants (other than MAO inhibitors)
  - Thyroid hormones
  - Atypical antipsychotics (e.g., quetiapine); Note: Clozapine is allowed, but must be stable for at least 5 months prior to Screening. In addition, the subject must not have had any episodes of neutropenia or severe infections since starting clozapine as confirmed by the clozapine-prescribing physician and must follow the clozapine prescribing information with regards to monitoring of white blood cell count.
  - Benzodiazepines and other sedatives/hypnotics  
Note: Intermittent (as needed) use of benzodiazepines and other sedative/hypnotics is allowed only if the drug has a half-life of less than 6 hours and it is not taken within 5 half-lives prior to cognitive testing.
- 4) Subject is 50 to 85 years of age, inclusive, at the time of the Screening Visit.
- 5) Female subjects must be:
  - a) Of non-childbearing potential (i.e., any female who is post-menopausal [greater than 1 year without menstrual period in the absence of hormone replacement therapy]) or surgically sterile; or,
  - b) If pre-menopausal or menopausal for 1 year or less, must have a negative pregnancy test and must not be lactating at Screening. Female subjects of childbearing potential and who are sexually active are required to practice highly effective methods of birth control during the course of the study. Female subjects for whom menopausal status is in doubt, in the opinion of the investigator, will be required to use a highly effective form of birth control. Highly effective forms of birth control are defined as methods that have a failure rate of less than 1% per year when used correctly and consistently and include:.

- combined (estrogen and progestogen containing) hormonal contraception associated with inhibition of ovulation; oral, intravaginal, or transdermal
  - progestogen-only hormonal contraception associated with inhibition of ovulation; oral, injectable, or implantable
  - intrauterine device (IUD)
  - intrauterine hormone-releasing system ( IUS)
  - bilateral tubal occlusion
  - vasectomised partner
  - sexual abstinence
  - double barrier method: condom and an occlusive cap (diaphragm or cervical/vault caps) with a vaginal spermicidal agent (foam/gel/film/cream/suppository)
- c) Subjects who have a positive pregnancy test during the study or become pregnant during the study will be discontinued.

Note: Male subjects who are sexually active and whose partner is of child-bearing potential are also required to use an adequate form of birth control including at least 1 barrier method.

- 6) Subject has the ability to comply with procedures for cognitive and other testing in the opinion of the investigator.
- 7) Subject must be able to ingest pills (in tablet form) whole.
- 8) Subject lives with (or has substantial periods of contact with) a regular caregiver who is willing to attend visits, oversee the subject's compliance with protocol-specified procedures and study medication, and report on subject's status, and who has substantial contact with the subject. If the caregiver does not cohabit with the subject, he/she ideally should have a minimum of 10 hours total and at least 3 days contact with the subject per week. Prior to randomization, study staff will review eligibility of non-cohabitating caregivers. Every effort should be made to have the same caregiver throughout the study.
- 9) Subject has provided full written informed consent prior to the performance of any protocol-specified procedure; or if unable to provide informed consent due to cognitive status, subject has provided assent and a legally acceptable representative (LAR) has provided full written informed consent on behalf of the subject.
- 10) Caregiver has provided full written informed consent on his/her own behalf prior to the performance of any protocol-specified procedure.
- 11) The subject's general health status is acceptable for participation in a 24-week study in the opinion of the investigator.

### **6.3. Exclusion Criteria**

A subject will not be eligible for inclusion in this study if any of the following criteria apply:

Other Causes for Dementia:

- 1) Atypical clinical features or clinical course of dementia that would lead the investigator to conclude primary symptoms are more likely explained by an alternate dementia diagnosis including, but not limited to, Parkinson's disease dementia, vascular dementia, frontotemporal dementia, or Alzheimer's disease dementia.
- 2) A CT or MRI scan performed within the past 12 months or at Screening that is indicative of any other CNS disorder that, in the opinion of the investigator, could be interpreted as the primary cause of dementia (e.g., cerebrovascular disease [transient ischemic attack, stroke, hemorrhage]; structural or developmental abnormality; epilepsy; infectious, or degenerative or inflammatory/demyelinating CNS conditions) or any other history and/or evidence to suggest the same.
- 3) Evidence of the following disorders where this is thought to be the cause of, or to contribute to the severity of, the subject's dementia: current vitamin B12 deficiency, hypothyroidism, neurosyphilis, HIV dementia, or Korsakoff's encephalopathy.
- 4) Focal findings on the neurological exam (excluding changes attributable to peripheral injury) that are inconsistent with a primary diagnosis of DLB.

Confounding Medical Conditions

- 5) History of schizophrenia, major depressive episode in the past 6 months, or any other significant psychiatric condition such as bipolar affective disorder that in the opinion of the investigator would interfere with participation in the study or could affect performance on outcome measures.
- 6) Significant suicide risk as defined by (1) suicidal ideation as endorsed on items 4 or 5 on the C-SSRS within the past year, at Screening or since the last visit at Baseline or; (2) suicidal behaviors within the past year or; (3) clinical assessment of significant suicidal risk during subject interview.
- 7) History of epilepsy or unexplained seizure in the past 5 years or history of significant head trauma with loss of consciousness in the past 5 years.
- 8) History of malignancy during the 5 years before Screening. History of basal cell carcinoma and melanoma in situ are permitted. History of other cancers currently in a non-active state may be acceptable after review with the Medical Monitor.
- 9) Any clinically relevant concomitant disease including unregulated diabetes, progressive liver or kidney dysfunction, history of myocardial infarction or unstable angina within 6 months of Screening, history of more than one myocardial infarction within 5 years of Screening, history of clinically significant stroke, history or evidence of HIV infection, or any other medical or psychiatric condition, which, in the opinion of the investigator, makes the subject unsuitable for inclusion in the study.
- 10) History of alcohol use disorder or other substance abuse disorder (excluding tobacco use), according to the DSM-5 in the past 10 years.

Concomitant Medications

- 11) Participation in another investigational drug or device study during the 30 days prior to the Screening Visit (Visit 1), or within 5 half-lives of use of the investigational drug prior to the Screening Visit, whichever is longer. In addition, subjects who were previously screened for another study in DLB but failed the entry criteria for that study may be screened with no time delay prior to the Screening Visit, provided that, in the opinion of the investigator, and after consultation with the Medical Monitor as needed, there is a realistic possibility that the subject would be eligible.
- 12) Treatment with any concomitant medications as detailed in Table 1. Prohibited medications as outlined in Table 1 unless otherwise specified, need to have been discontinued for 5 half-lives prior to screening and assessed as no longer clinically necessary for the subject.

Unacceptable Tests/Laboratory Values

- 13) Alanine transaminase (ALT) and/or aspartate aminotransferase (AST)  $\geq 2.0$  times upper limit of normal (ULN) at Screening.
- 14) Total bilirubin over 1.5 x ULN at Screening except due to documented Gilbert's disease or evidence of Gilbert's disease on Screening laboratory assessments.
- 15) Calculated creatinine clearance  $< 40$  mL/min (Cockcroft-Gault formula) at Screening:  
Adult Males:  $[(140 - \text{age in years}) \times (\text{weight in kg})] \div 72 \times \text{serum creatinine in mg/dL}$   
Adult Females:  $0.85 \times [(140 - \text{age in years}) \times (\text{weight in kg})] \div 72 \times \text{serum creatinine in ng/dL}$
- 16) Positive hepatitis B surface antigen or hepatitis C antibody test at Screening.
- 17) Confirmed corrected QT interval (QTc) value greater than or equal to 450 msec for males or greater than or equal to 470 msec for females at Screening. Subjects with a QRS value greater than 120 msec and subjects with QTc value less than 500 msec may be eligible following discussion with the Medical Monitor.

Other

- 18) Previous exposure to RVT-101 (SB742457).
- 19) Subject is unable to take study medication as prescribed throughout the study (with assistance is acceptable) or is at risk of non-compliance with study medication or procedures as determined by the investigator.
- 20) Subject is unable to complete the CDR computerized assessment system during the Screening period (repeat assessments allowed) or, in the investigator's opinion, the subject will not be able to consistently complete the CDR computerized assessment system throughout the course of the study. Subjects who are unable to complete the CDR computerized assessment system during the Run-In or Baseline visits will not be randomized. If a subject is unable to complete the CDR computerized assessment system testing during one of the study visits, testing may be rescheduled within the Visit window.

- 21) Subject or caregiver is an immediate family member or employee of the participating investigator, any of the participating site staff, or of the sponsor study staff.
- 22) Subject was prescribed and initiated cognitive tasks for cognitive rehabilitation under medical supervision in the 2 months prior to Screening or plans to initiate a program of cognitive rehabilitation during the course of the study. Subjects who are treated with stable programs of cognitive rehabilitation for at least 2 months prior to Screening with no plan to change or discontinue the cognitive rehabilitation for the duration of the study are acceptable.
- 23) Subject has initiated a program of neurostimulation in the past 2 months or plans to initiate a program of neurostimulation during the course of the study. Subjects who are treated with stable programs of neurostimulation for at least 2 months prior to Screening with no plans to change or discontinue the neurostimulation for the duration of the study are acceptable.

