**Table 16: Serum Chemistry Potentially Clinically Significant Criteria (Study RVT-101-2001)**

Parameter	Gender	Low PCS	High PCS
Alanine aminotransferase (U/L)	Male	NA	133
	Female	NA	100
Albumin (g/L)	Male/Female	29	NA
Alkaline phosphatase (U/L)	Male	NA	323
	Female	NA	246
Aspartate aminotransferase (U/L)	Male	NA	118
	Female	NA	103
Direct bilirubin (umol/L)	Male/Female	NA	7.7
Total bilirubin (umol/L)	Male/Female	NA	30.8

Calcium (mmol/L)	Male/Female	1.99	2.91
Creatinine (umol/L)	Male	NA	174
	Female	NA	147
GGT (U/L)	Male	NA	136
	Female	NA	93
Creatinine clearance (mL/min)	Male/Female	29	NA
Random glucose (mmol/L)	Male/Female	2.9	NA
Potassium (mmol/L)	Male/Female	3.4	5.6
Sodium (nmol/L)	Male/Female	129	151

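### Exclusion criterion 15 prints the Cockcroft-Gault formula without a bracket round its denominator and in different creatinine units for men and women, so the renal cut-off cannot be applied safely as printed

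*Protocol*

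**What the plan says.** Protocol section 6.3, criterion 15, makes calculated clearance below 40 an exclusion and identifies the method: "mL/min (Cockcroft-Gault formula) at Screening". It then prints one line per sex. Both share the numerator "140 - \text{age in years}) \times (\text{weight in kg", closed in square brackets, followed by a division sign.

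- Male line, after the division sign: "72 \times \text{serum creatinine in mg/dL".
- Female line, with a leading factor of 0.85: "72 \times \text{serum creatinine in ng/dL".

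Neither line brackets the product of 72 and creatinine. The lines also differ in unit, mg/dL against ng/dL.

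This is the only clearance formula in either document. Protocol Table 5 lists creatinine, without a unit, and does not list clearance. SAP Table 16 has a low-side limit for clearance, "Creatinine clearance (mL/min) Male/Female 29 NA", and high-side limits for creatinine (174 umol/L for men, 147 umol/L for women). It cites no formula.

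**The concern.** Criterion 15 is a numeric safety threshold, and section 8 of the protocol allows no waivers except for immediate safety concerns. A site applying the criterion has only the printed expression and the name of the method.

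There are two separate defects. First, by ordinary operator order an unbracketed division followed by a multiplication makes creatinine a multiplier. Clearance would then rise as creatinine rises, and the cut-off would fall on the wrong side. Second, the two lines are meant to differ only by the factor 0.85, so the two units cannot both be right.

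At stake is whether the renal exclusion sorts subjects in the intended direction. No endpoint, power or alpha figure depends on it.

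**Working it through.** **Plan's own figure.** The documents give no worked clearance value, so there is nothing to reproduce. The check evaluates the printed expression under its two possible readings.

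**Inputs.** From criterion 15: numerator (140 − age) × weight, constant 72, female factor 0.85, threshold 40 mL/min. From section 6.2, the age range: "Subject is 50 to 85 years of age, inclusive, at the time of the Screening Visit". Body weight and creatinine are assumptions, because the documents give no distribution: 60 to 80 kg and 0.5 to 2.5 mg/dL. Unit conversion: 1 mg/dL = 1,000,000 ng/dL.

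**Formulas.** Let k = (140 − age) × weight ÷ 72, times 0.85 for women.
- Reading A, left to right: clearance = k × creatinine. Excluded when creatinine is below 40 ÷ k.
- Reading B, everything after the division sign as divisor: clearance = k ÷ creatinine. Excluded when creatinine is above k ÷ 40.

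**Male line, 75 years, 70 kg.** (140 − 75) × 70 = 4550, and k = 4550 ÷ 72 = 63.19.

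| Creatinine (mg/dL) | Reading A | Reading B |
|---|---|---|
| 0.6 | 63.19 × 0.6 = 37.9, excluded | 63.19 ÷ 0.6 = 105.3, admitted |
| 1.0 | 63.2, admitted | 63.2, admitted |
| 2.0 | 63.19 × 2.0 = 126.4, admitted | 63.19 ÷ 2.0 = 31.6, excluded |

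Reading A excludes this man below 40 ÷ 63.19 = 0.63 mg/dL. Reading B excludes him above 63.19 ÷ 40 = 1.58 mg/dL. Between those values both readings admit him.

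**Other male profiles.**

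| Age, weight | k | Reading A excludes below | Reading B excludes above |
|---|---|---|---|
| 50 y, 80 kg | 100.00 | 0.40 mg/dL | 2.50 mg/dL |
| 75 y, 75 kg | 67.71 | 0.59 mg/dL | 1.69 mg/dL |
| 85 y, 60 kg | 45.83 | 0.87 mg/dL | 1.15 mg/dL |

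The readings disagree over the widest part of the assumed creatinine range in old, light men.

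**Female line as printed, 75 years, 70 kg.** k = 0.85 × 63.19 = 53.72. The same two creatinine values in ng/dL are 600,000 and 2,000,000.
- Reading A: 53.72 × 600,000 ≈ 3.2 × 10⁷ and 53.72 × 2,000,000 ≈ 1.1 × 10⁸ mL/min. Both are admitted.
- Reading B: 53.72 ÷ 600,000 ≈ 9.0 × 10⁻⁵ and 53.72 ÷ 2,000,000 ≈ 2.7 × 10⁻⁵ mL/min. Both are excluded.

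The result does not depend on the profile. For a woman of 85 years and 60 kg, k = 38.96. At the lowest assumed creatinine, 500,000 ng/dL, reading A still gives about 1.9 × 10⁷ mL/min. For a woman of 50 years and 80 kg at that creatinine, k = 85 and reading B gives 0.00017 mL/min.

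**Intended direction.** SAP Table 16 flags high creatinine and low clearance. Clearance must therefore fall as creatinine rises, which only reading B does. With mg/dL, reading B gives values in the tens to low hundreds of mL/min, the scale on which limits of 40 and 29 have meaning. With ng/dL, neither reading comes near that scale.

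**The case against.** The strongest reply is that this is a missing bracket and not a reversed rule. The criterion names its method, the printed terms are that method's terms set inline, and SAP Table 16 confirms the direction. That stands: a reader might infer that the protocol definitely multiplies by creatinine, and the documents do not support that for the male line. The reply does not rescue the female line, where the unit fails whichever way the expression is grouped.

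A second reply is that the fault may lie in the text extraction. The string is mark-up reconstructed from a PDF, and a stacked fraction, a bracket or a letter could have been lost or misread. SAP Table 16 shows a similar oddity, sodium in nmol/L with limits of 129 and 151 while potassium and calcium are in mmol/L. This cannot be excluded and must be checked first. Against it, the numerator brackets survived on both lines while the denominator bracket is absent from both.

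Third, there are other safeguards. Criterion 9 excludes progressive kidney dysfunction, section 6.1 requires physician input on medical questions of eligibility, section 6.4 allows sponsor review of selected subjects, and creatinine is measured at each of the first three visits. These make an unnoticed error less likely. They do not replace a numeric limit, and the sponsor review is optional.

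Four further inferences go beyond the documents:
- That the printed rule admits impaired women and excludes healthy ones. That two-way pattern appears for women only if mg/dL is put in place of the printed ng/dL and the line is read left to right.
- That the SAP's table of potentially clinically significant values would run backwards. Table 16 does not cite the protocol expression, and nothing says clearance will be programmed from it.
- That umol/L in Table 16 is a third conflicting unit. That table uses SI units for other analytes too, so umol/L is consistent there.
- That ineligible subjects were enrolled. Nothing shows that any site calculated clearance by hand from the printed line.

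**Conclusion.** The point holds as a notation and unit defect in a safety eligibility rule. The male line is ambiguous: left to right it reverses the 40 mL/min rule, while the named method and SAP Table 16 indicate that creatinine is meant to be in the divisor. The female line, as printed in ng/dL, does not work on either reading, since it admits every woman or excludes every woman.

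The male figures rest on assumed weights and creatinine values, with ages inside the protocol range. The female conclusion holds across all the assumed profiles, because the unit shifts the result by a factor of a million. Both conclusions depend on the extracted text matching the source PDF. No mis-enrolment is shown. The correction is small but worth making, because the criterion decides who is exposed to study drug.

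**What to change.** 1. Check criterion 15 in the source PDF for a lost bracket or a misread unit.
2. If the text is as extracted, reconcile the printed expression with the formula the criterion names by bracketing 72 × serum creatinine as the denominator on both lines.
3. Use one creatinine unit on both lines.
4. Recheck screened subjects only where clearance was hand-calculated from the printed expression.

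The 40 mL/min threshold stays as it is. The cost is a correction to one criterion at the next protocol amendment, plus a short recheck of screening values if any site used the printed expression by hand.
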